- ^m In addition to a brief physical examination, a full neurological examination should be performed for any study participant who experiences severe and/or serious headache and for any study participant who experiences features suggestive of aseptic meningitis (see Appendix 14 [Section 10.14]). For details of the assessments included in these examinations, see Section 8.2.5. For additional assessments that may be required in case of these AESM, see Section 1.3.1 (Table 1-4).
- ⁿ Single 12-lead ECGs, which will be read locally.
- ^o Return of used and unused vials as well as all equipment and ancillary materials used for IMP administration.
- P The timing between Screening and the Baseline Visit needs to be a minimum of 14 days to confirm eligibility and to ensure all prerequisites are met.
- ^q Not applicable for study participants not considered eligible for self-administration, who will continue receiving IMP administered by the HCP at the study site (for additional details, see Section 4.1).
- ¹ Exploratory biomarker samples will be taken predose at Baseline (Day 1) for all study participants. In study participants who experience severe and/or serious headaches or features suggestive of aseptic meningitis, samples should also be collected 4 hours after the onset of the event, or otherwise as soon as possible within 72 hours after the onset of the event. For additional assessments that may be required in case of these AESM, see Section 1.3.1 (Table 1-4).
- ^s Participants completing all Treatment Periods, including the EOT Visit, and moving on to either a post-trial access program or commercially available rozanolixizumab during the SFU Period must undergo an earlier EOS Visit prior to this move (see Section 4.4 and Section 6.8).

Confidential Page 23 of 124

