Treatment Period of MG0020 starts with standardized trainings over the course of a Training Period when the study participant is trained on both the manual push and the syringe driver administration methods. During the Training Period, the study participant doses of rozanolixizumab SC and should practice both methods of administration at the study site. To act as a reference for the preference question (HCP vs selfadministration) and to demonstrate subcutaneous infusions of rozanolixizumab, the first administration will be imperatively performed by the HCP. For all remaining training visits, the study participant should perform as many self-administrations as possible (under HCP supervision) depending on their training status. Self-administration under HCP supervision or administration by HCP will be documented in the CRF. At Visit 8 (), after the completion of the Training Period and following the investigator's confirmation of the eligibility to perform self-administration, the study participant will be randomized 1:1 to either the syringe driver or to the manual push administration method. After completing Self-administration Period 1 (at), the study participant will crossover to the alternative administration method, entering Self-administration Period 2 (Visit 14 [see the study schema in Section 1.2). A final release of the study participant for home self-administration will be based on a successful demonstration of self-administration using the assigned mode of administration (manual push or syringe driver use) at Visit 9 (and Visit 15 (), respectively. Study participants who cannot be confirmed eligible for self-administration will not perform self-administration and can continue to be treated on-site per protocol based on investigator

Confidential Page 31 of 124

decision. Additionally, if a study participant becomes no longer eligible for self-administration during the Self-administration Periods, he/she can continue to be treated by HCP on-site per protocol based on investigator decision. The study medication administration can be performed either via syringe driver or manual push. Adverse events, concomitant medication, vital signs, ECG, suicidality, blood and urine samples for safety laboratory tests, pregnancy tests, and IgG will continue to be collected from these study participants until End of Study Visit/Early Withdrawal Visit. Handling of replacement participants is described in Section 7.2.

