6.5.4 Rescue medication

The study site will supply rescue therapy that will be obtained locally. Rescue therapy will be given as per standard of care and at the discretion of the investigator. Study participants who continue to experience moderate to severe symptoms despite treatment with rozanolixizumab may receive treatment with the following as rescue therapy:

- Intravenous Ig (ATC code: [Immunoglobulins, normal human])
- Subcutaneous Ig (ATC code: [Immunoglobulins, normal human])
- Plasma exchange or plasmapheresis
- Intravenous corticosteroids at a higher dose than previous oral dose (ATC code: [Corticosteroids for systemic use, plain])

Study participants who received treatment with rescue therapy will be withdrawn from the study.

The date and time of rescue medication administration as well as the name and dosage regimen of the rescue medication must be recorded.

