# 3 POPULATIONS FOR ANALYSIS

- Enrolled Set (ES): All study participants who have signed the informed consent form.
- Safety Set (SS): All study participants who received at least 1 dose of investigational medicinal product (IMP) (partial or full). Analysis of this set will be according to the administration method the participants actually used and will be used for analyses of safety and demography outcomes as required.
- Randomized Safety Set (RSS): All participants who are included in SS and were randomized. Analysis of this set will be according to the administration method the participants actually used and will be used for analyses of safety, demography, and efficacy/outcomes.
- Full Analysis Set (FAS): All participants who are included in SS, were randomized and completed both Self-administration Periods. Both Self-administration Periods will be considered as complete if self-administration occurred on Visits 13 and 19 in accordance with the randomization scheme.

#### STATISTICAL ANALYSES 4

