#### 4.4.2 MG-ADL

The symptom changes in study participants with gMG will be evaluated. The complete list of MG-ADL items and scores are provided in Table 6-5. The total score will be calculated according to the rules set down in Section 6.11.

itzation The MG-ADL total score and change from Baseline will be summarized at each visit for the RSS by sequence using descriptive statistics.

Worsening in MG-ADL score will be defined by a >2 points increase from Baseline at any timepoint during the treatment period. The number and proportion of study participants experiencing a worsening of their MG-ADL symptoms during the study will be summarized overall for the RSS. This table will also include the number, proportion and 90% CI of study participants experiencing MG-ADL worsening, considering the last available measurement in the study before the End of Study Visit (Visit 21). The 90% CI will be estimated using the Wilson method (without continuity correction) [2].

Since MG-ADL is completed predose, if time of collection is missing for Visit 2, this will be considered as the Baseline assessment.

Line plots of mean MG-ADL total score and mean change from baseline over time by sequence will be presented for the RSS. Spaghetti plots of MG-ADL total score and change from baseline over time will be presented for the RSS.

By-participant listings of MG-ADL values will be provided for the SS.

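### MG-ADL collection stops when self-administration eligibility is lost and is not scheduled at Early Withdrawal, so the planned worsening proportion cannot see later deterioration in those participants

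*SAP*

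**What the plan says.** SAP 4.4.2 reports two worsening measures, both against the Visit 2 Baseline. The first is worsening at any timepoint in the treatment period: participants "experiencing a worsening of their MG-ADL symptoms during the study will be summarized" overall for the RSS. The second uses the last available score before Visit 21 and carries a 90% Wilson interval. SAP Section 3 defines the RSS as "All participants who are included in SS and were randomized", so it keeps people who later stop self-administering or withdraw.

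Protocol Table 1-3 schedules MG-ADL at V1, V2, V8, V10 to V14 and V16 to V19. Each entry from V8 carries footnote q: "Not applicable for study participants not considered eligible for self-administration, who will continue receiving IMP administered by the HCP at the study site". Protocol 4.1 lists what is still gathered from such participants, ending with "pregnancy tests, and IgG will continue to be collected from these study participants until End of Study Visit/Early Withdrawal Visit". MG-ADL is not on that list, nor on the matching list in SAP 4.1.7.

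On rescue, Protocol 6.5.4 says: "Study participants who received treatment with rescue therapy will be withdrawn from the study". Protocol 7.2 refers to Table 1-3 for what is collected at the Early Withdrawal Visit, and the MG-ADL cell in the V20/Early Withdrawal column is empty.

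**The concern.** The analysis claims to cover the whole study and every randomized, treated participant. The data cover only the time during which a participant remains eligible to self-administer and has not withdrawn. One of the exits is connected with symptoms: rescue is given for continuing moderate to severe symptoms. The other, loss of eligibility, may or may not be.

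The plan treats IgG differently. IgG continues after self-administration stops (Protocol 4.1, SAP 4.1.7), and SAP 4.4.3 has an explicit rescue rule for it. SAP 4.4.2 has no rule for MG-ADL after either event. SAP 4.4.3 then plots MG-ADL and IgG together by sequence, although the two can rest on different participants at later visits. What is at stake is the stated objective of evaluating symptom changes, and a reader's ability to trust a low worsening rate.

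**Working it through.** **Plan's own figure.** The documents give no expected MG-ADL worsening rate. Their only precision figures (Protocol Table 9-1, SAP Table 5-1) concern the primary endpoint. Exact Clopper-Pearson 90% limits at 24/30, 27/30 and 29/30 reproduce them: 64.3 to 90.9, 76.1 to 97.2 and 85.1 to 99.8. Only N = 30, the planned minimum, is carried forward.

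**Step 1: scores available.** A full course has 10 scheduled post-baseline assessments: V8, V10, V11, V12, V13, V14, V16, V17, V18, V19. The V9 cell shows only stray print in the extracted table; it is read as empty, like its counterpart V15.

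| Eligibility lost | Scheduled scores obtained |
|---|---|
| at V9 | 1 of 10 (V8) |
| after V13 | 5 of 10 |
| after V15 | 6 of 10 |

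For withdrawal after rescue, the last score is from the last scheduled MG-ADL visit attended. SAP 4.1.3 maps Early Withdrawal assessments to the next scheduled visit, but there is no scheduled MG-ADL to map.

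**Step 2: direction, any timepoint.** A participant counts as worsened if the largest observed increase from Baseline meets the threshold. The largest value over a subset of visits cannot exceed the largest over all visits. Truncation can therefore remove a worsening but not create one. With the RSS as a fixed denominator, the bias is downward or zero. This holds whether the threshold is at least 2 points (Protocol 9.3.3) or more than 2 points, as the SAP text prints it.

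**Step 3: direction, last available.** The score used is the last one before the stop. A participant who worsens afterwards is counted as not worsened. One whose last score showed worsening, and who improves later on HCP dosing, stays counted as worsened. The error can go either way.

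**Step 4: size.** Each missed case shifts a proportion by 1/N = 1/30 = 3.3 points. The Wilson 90% interval has centre (p + z²/2n)/(1 + z²/n) and half-width z·√(p(1−p)/n + z²/4n²)/(1 + z²/n), with z = 1.645. The counts below are assumed, for illustration only, with 3 of 30 recorded as worsened. The intervals apply if the last-available measure has these counts.

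| Status with complete collection | Count | Proportion | 90% Wilson CI |
|---|---|---|---|
| one recorded case later improved (last available only) | 2/30 | 6.7% | 2.2 to 18.3 |
| as recorded | 3/30 | 10.0% | 4.1 to 22.6 |
| 1 missed | 4/30 | 13.3% | 6.1 to 26.6 |
| 2 missed | 5/30 | 16.7% | 8.4 to 30.5 |
| 3 missed | 6/30 | 20.0% | 10.7 to 34.3 |

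**The case against.** The strongest reply is that little is lost. MG-ADL is an 'other' endpoint, described in Protocol 8.2 as symptom monitoring and not as a measure of treatment benefit, in a study without hypothesis testing. Protocol 9.3.3 framed worsening as occurring in the Self-administration Period, by method, so collecting the scale only while people self-administer is coherent with that. Rescue therapies are summarized and listed (SAP 6.7.2), discontinuation reasons are tabulated (SAP 6.3), and MG-ADL is listed by participant. This stands as a limit on importance. It does not reconcile SAP 4.4.2, which has moved to the whole study and whole RSS, with the schedule.

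A reader might infer several stronger things that the documents do not support.

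- That these participants drop out of the proportion. They do not: once randomized they stay in the RSS and their earlier scores count. Only later worsening is missed.
- That those losing eligibility are the ones getting worse. This is an inference. Release for home dosing depends on demonstrated technique (Protocol 4.1), and a caregiver withdrawing consent also leads to on-site dosing (Protocol 10.1.3).
- That a rescued participant's last score always precedes the deterioration. Doses are 5 to 9 days apart and MG-ADL is taken at most dosing visits from V8, so the gap is short. Continuing symptoms may already be recorded, or may involve no increase from Baseline.
- That the last-available proportion is necessarily too low. Step 3 shows otherwise.
- That AE tables must miss the same events. Protocol Appendix 3 excludes expected disease symptoms, but it also counts exacerbation of a pre-existing condition as an AE.
- That the bias is a particular number of points. No rate of lost eligibility or rescue is given.

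Timing is also a fair objection. Amendment 5 (30 Nov 2023) says all 75 participants had been screened. Up to 4 weeks of screening plus 29 − 4 − 7 = 18 weeks of treatment runs to about 2 May 2024, barring rescreening or replacements. The SAP amendment is dated 03 May 2024, so a schedule change may recover little in this study.

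**Conclusion.** The point holds as a mismatch between what SAP 4.4.2 reports and what Table 1-3 collects. The any-timepoint proportion can only be understated, by 3.3 points per missed case at N = 30 and less with a larger RSS. The last-available proportion and its 90% CI rest on truncated scores; their error has no fixed sign, though it is probably toward too few worsened among rescued participants. The total size cannot be computed, because the documents give neither the number who lose eligibility or are rescued nor how many of them worsen unseen. The conclusion assumes that Table 1-3 was followed as written and that the denominator is the full RSS. The symptom-change objective is affected; the primary endpoint is not.

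**What to change.** **Collection.** In Table 1-3, remove footnote q from the MG-ADL row and add MG-ADL to the V20/Early Withdrawal column. Add MG-ADL to the continued-collection lists in Protocol 4.1 and SAP 4.1.7, and state in SAP 4.4.2 that these scores enter both worsening measures.

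**Where data are already collected.** In SAP 4.4.2, report how many RSS participants have MG-ADL cut short by loss of eligibility or by early withdrawal, and how many scores each contributed. Add a sensitivity analysis that counts receipt of Protocol 6.5.4 rescue therapy as worsening. Keep the score-based measure as the main one: making rescue part of it would turn a scale result into a composite, which is a debatable choice.

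**Cost.** One 8-item questionnaire at visits these participants already attend, wording changes in the two documents, and one extra table line with a sensitivity row. The reported worsening rate may become less favourable.

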#### 4.4.3 Pharmacodynamic

The pharmacodynamics of rozanolixizumab will be assessed considering the total IgG level over time. Total serum IgG concentrations including observed values and percentage change from baseline will be summarized overall for the Training period for the SS and by sequence for the RSS. For the analysis of the IgG data, in case rescue therapies are taken, the data up to (not including) the start date of rescue therapy and the data 8 weeks after the start date of rescue therapy will be utilized for the summary tables, ie the data from (including) start date of rescue therapy, to 8 weeks after start date of rescue therapy will be excluded from summary analysis. In cases where a study participant drops out, no missing value imputation will be performed for the IgG.

Line plots of median IgG concentrations and percentage change from baseline over time by sequence will be presented for the RSS. Spaghetti plots of IgG concentrations and percentage change from baseline over time will also be presented for the RSS.

A line plot presenting mean change from baseline in MG-ADL total score and median percentage change from baseline in IgG concentrations will be produced by sequence for the RSS.

In addition, a plot displaying individual percentage change from baseline in IgG concentrations, change from baseline in MG-ADL total score and duration of infusion will be produced for the RSS.

Total serum IgG concentrations will be listed by participant for the SS.

IgG laboratory assessments are performed predose.

## 4.4.4 Immunogenicity

The immunogenicity of rozanolixizumab will be assessed following subcutaneous selfadministration.

Evaluation of rozanolixizumab immunogenicity will be performed using data from all evaluable study participants in the SS, defined as all study participants who have an evaluable pretreatment (baseline) sample (negative or positive ADA sample status), and at least 1 evaluable post-baseline value. Study participants with an evaluable pretreatment (baseline) sample but without a single evaluable sample taken post-baseline will be included in the reporting of pre-existing ADA but excluded from all other immunogenicity analyses.

### ADA Sample Status

- The ADA sample status will be determined for the pre-treatment (Baseline) and posttreatment (post-Baseline) visits where samples are taken for ADA analysis. The classifications below are made under the assumption that the rozanolixizumab concentrations (which are not measured in this study) are equal or below the validated drug tolerance limit of the ADA assay (200µg/mL rozanolixizumab) allowing detection of 100ng/mL ADA
- Sample values that are either 'negative screen' or the combination of 'positive screen' and 'negative immunodepletion' will be defined as **ADA negative**
- Sample values that are 'positive screen' and 'positive immunodepletion' will be defined as ADA positive
- Samples that could not be tested for ADA status due to inadequate sample volume, mishandling, or errors in sample collection, processing, storage, etc, will be defined as **Missing**.

## ADA Participant Status

The ADA participant status will be classified on study participant and group level as outlined below (Shankar et al. 2014; Rup et al, 2015). A description of how study participants will be categorized for the immunogenicity assessment is provided in Table 4-2

Individual study participants will be assessed for ADA participant status, composed of 6 categories: ADA negative, and ADA positive, whereby a positive participant's status is determined as originating from a treatment-induced, boosted, reduced or unaffected ADA response.

Study participants who are identified as being treatment-induced or treatment-boosted ADApositive will be grouped as treatment-emergent (TE)-ADA positive participants. Study participants who are identified as being treatment-reduced or treatment-unaffected ADA-positive will be grouped as non-TE-ADA positive participants.

The individual and combined ADA participant categories will be derived and summarized through each scheduled assessment visit unless specified otherwise. Post-baseline time points where no ADA sample was collected, will be ignored for the categorization.

Classification	Classification Label	Definition
Individual partici	pant categories	
1	Pre-ADA negative – treatment induced ADA negative (ADA-NEG)	Study participants who have an ADA negative sample at Baseline and at all sampling points post-Baseline up to the timepoint of interest.
2	Inconclusive	Study participants who have an ADA positive or negative Baseline sample and some post-Baseline samples are missing, while other post-Baseline samples are ADA negative up to the timepoint of interest.
3	Pre-ADA negative – treatment induced ADA positive (TI- POS)	Study participants who have an ADA negative sample at Baseline and have at least one ADA positive sample at any sampling point post- Baseline up to the timepoint of interest.
4	Pre-ADA positive – treatment boosted ADA positive (TB- POS)	Study participants who have an ADA positive sample at Baseline and at least one ADA positive sample at any sampling point post-Baseline up to the timepoint of interest, with increased titer values compared to Baseline (greater than a predefined fold difference increase from Baseline value which will be defined within the validation of the assay i.e. MSR of the assay).
5	Pre-ADA positive – treatment reduced ADA positive (TR- POS)	Study participants with an ADA positive sample at Baseline, and ADA negative samples at all sampling points post-Baseline up to the timepoint of interest.
	Pre-ADA positive – treatment unaffected ADA positive (TU-POS)	Study participants with an ADA positive sample at Baseline and an ADA positive sample at any sampling point post-Baseline up to the timepoint of interest, with titer values of the same magnitude as Baseline (less than a predefined fold difference from the Baseline value which will be defined within the validation of the assay, i.e. MSR of the assay  ).
Combined parti	cipant categories	
300 36	Treatment emergent ADA positive (TE-POS)	Includes study participants who are treatment induced ADA positive (category 3) or treatment boosted ADA positive (category 4).
8	Non-treatment emergent ADA positive (Non-TE-POS)	Includes study participants who are treatment reduced ADA positive (category 5) or treatment

# Table 4–2: Terms and Definitions for ADA Status Evaluation in Study Participant

Classification	Classification Label	Definition
i		

 The fold difference increase from baseline value, i.e. the minimum significant ratio (MSR=1.36) determined during assay validation, will be reported in the relevant tables, listings and figures. It reflects the fold difference in titer level that considered higher than the assay variation in titer determination.

The following tables will be produced:

- 1.3t101 Number and percentage of study participants with ADA (positive, negative, missing sample) status at the time of each visit will be summarized by self-administration sequence and overall for the RSS. Denominator is the number of study participants having a non-missing result at that visit.
- Number and percentage of study participants in each of the individual and combined ADA participant status categories presented in Table 4-2 will be summarized by selfadministration sequence and overall for the RSS.
- Total prevalence of pre-existing ADA, defined as number and percentage of participants having an ADA positive sample status at baseline, with the denominator being the total number of study participants having an evaluable sample result at baseline will be summarized by self-administration sequence and overall for the RSS. Missing samples will not be included in the denominator.

The following figures will be produced and will be based on the RSS:

Individual time course plots for ADA positive study participants with at least one ADA positive sample, representing ADA titers (on log-scale), and the percentage CFB for total IgG. The sub-title of the graph will include the study participant number, bodyweight category, and individual ADA participant category (3, 4, 5, 6). The dosing will be represented in the x-axis with bars/arrows at the time of dose.

A by-participant listing by period, self-administration method and timepoint, of ADA sample status and titer will be produced

